10.1 General Considerations

Safety parameters will be evaluated for the safety analysis data set.

All safety summaries will be tabulated by treatment arm (including pooled active treatment arms).

10.2 Adverse Events

Adverse events (AEs) are classified according to the Medical Dictionary for Regulatory Activities (MedDRA). The version of MedDRA will be documented in the clinical report.

Written narratives will be issued for all serious AEs (including deaths) and AEs leading to withdrawal.

A pre-treatment adverse event is any untoward medical occurrence arising or observed between informed consent and administration of the IMP.

A treatment emergent adverse event is any adverse event occurring after the administration of the IMP and within the time of residual drug effect, or a pre-treatment adverse event or pre-existing medical condition that worsens in intensity after start of IMP and within the time of residual drug effect.

The time of residual drug effect is the estimated period of time after the end of the administration of the IMP, where the effect of the product is still considered to be present based on pharmacokinetic, pharmacodynamic or other substance characteristics. A generally accepted time for residual drug effect is 5 half-lives. The terminal half-life of the IMP is expected to be not more than 1.8 hours, and treatment-emergent AEs are defined as AEs occurring after the start of study drug infusion to within 12 hours after study drug infusion is stopped.

A post-treatment adverse event is any adverse event occurring after the residual drug effect period. Missing values will be treated as missing, except for causality, intensity, seriousness, and outcome of adverse events. A "worst case" approach will be used: if causality is missing, the adverse event will be regarded as related to the IMP; if the intensity of an adverse event is missing, the adverse event will be regarded as severe; if seriousness is missing the adverse event will be regarded as serious; if start date is missing or incomplete, worst case will be assumed and the AE will be regarded as treatment emergent (only if the incomplete start date is not compromised). If start date is completely missing, start date will be set as same day as start of treatment. If start date is incomplete, the date closest to start of treatment will be assumed, without compromising the incomplete data available on the start date; if outcome is missing and no date of outcome is present the outcome is regarded as 'not recovered'.

10.2.1 Overview of Adverse Events

AE overview summary tables will be prepared for treatment-emergent AEs and all AEs (treatment-emergent and non treatment-emergent) during the treatment period, including the number of

Date: 20 Nov 2017 E-Statistical Analysis Plan-17877; Ver.9.0

Supersedes: Ver. 8.0 Page 43 of 80

patients reporting an AE, the percentage of patients (%) with an AE, and the number of events (E) reported, for the following categories:

- Adverse events
- Deaths
- Serious adverse events
- Adverse events leading to discontinuation of IMP
- Severe and life threatening adverse events
- Adverse drug reactions

10.2.2 Incidence of Adverse Events

Adverse events will be summarised in a Table by SOC and PT for MedDRA. The Table will display the total number of patients reporting an AE, the percentage of patients (%) with an AE, and the number of events (E) reported. AEs will be presented by system organ class (SOC) sorted alphabetically and preferred term (PT) sorted in decreasing frequency of occurrence.

For both treatment-emergent AEs and all AEs (treatment-emergent and non treatment-emergent) during the treatment period, summary tables will be prepared for:

- All adverse events
- Adverse events with an incidence $\geq 5\%$ of patients in any treatment arm
- Non-serious adverse events with an incidence $\geq 5\%$ of patients in any treatment arm
- Critical adverse events (see Appendix 2 for details)
- Adverse events by causality (related/unrelated)
- Adverse events leading to death
- Adverse events by intensity
- Serious adverse events
- Adverse events leading to discontinuation of IMP (related/unrelated)

Supporting data listings will be provided for:

- All adverse events sorted by centre and patient no.
- All adverse events sorted by MedDRA Preferred Term
- Serious adverse events
- Adverse events leading to death
- Adverse events leading to discontinuation of IMP (related/unrelated)
- Post treatment-emergent adverse events.

Page 44 of 80

Furthermore, for both treatment-emergent AEs and all AEs (treatment-emergent and non treatment-emergent) during the treatment period, graphs showing the most frequent adverse events and the difference and 95% confidence interval between placebo and selepressin pooled will be presented for:

- All adverse events
- Adverse events with an incidence $\geq 5\%$ of patients in any treatment arm
- Critical adverse events (see Appendix 2 for details)
- Adverse events leading to death
- Serious adverse events

10.3 Safety Laboratory Variables

Baseline for all laboratory analyses will be the values obtained at the last assessment prior to (or at) the first dose of the investigational medicinal product (IMP). End of treatment period will include the last post-baseline observation during the trial up until Day 30.

Laboratory variables will be grouped under "Haematology", "Clinical Chemistry" or "Coagulation".

10.3.1 Summary Statistics

Mean change and mean percentage (%) change from baseline at end of treatment period will be presented for each laboratory variable. In addition, descriptive statistics, i.e., the number of patients with data, mean (standard deviation), median, interquartile range, minimum, and maximum values, will be presented for observed values and change from baseline at each time-point for each laboratory variable.

Furthermore, summary tables will be presented, displaying by time and laboratory parameter, the number of patients with a clinically significant result assessed as unanticipated.

Also, a summary table will be prepared for selected laboratory variables that display the number and percentage of patients in each treatment arm with X% increments (increase or decrease) from baseline at pre-specified timepoints and end of treatment period. The following categories for summary tables are defined:

• \leq -3*X%: Values with more than 3*X% decrease from baseline

• > -3*X% - -2*X%: Values with 2-3*X% decrease from baseline

• > -2*X% - -1*X%: Values with 1-2*X% decrease from baseline

• > -1*X% - 0*X%: Values with 0-1*X% decrease from baseline

• <0*X%- <1*X%: Values with 0-1*X% increase from baseline

Date: 20 Nov 2017 E-Statistical Analysis Plan-17877; Ver.9.0 Supersedes: Ver. 8.0

Page 45 of 80

• 1*X%- < 2*X%: Values with 1-2*X% increase from baseline

• 2*X%- < 3*X%: Values with 2-3*X% increase from baseline

• $\geq 3*X\%$: Values with more than 3*X% increase from baseline

The following key laboratory variables will be summarised:

• Hemoglobin: 20% change

• WBC: 50% change

• Platelets: 50% change

• Creatinine: 20% change

• Sodium: 5% change

• Lactate: 50% change

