10.4.1 Summary Statistics

Descriptive statistics, i.e., the number of patients with data, mean (standard deviation), median, interquartile range, minimum, and maximum values, will be presented for observed values and change from baseline at each time-point for each vital signs variable.

Furthermore, summary tables will be presented, displaying by time and vital signs parameter, the number of patients with a clinically significant result assessed as unanticipated.

Also, a summary table will be prepared for each vital signs variable that display the number and percentage of patients in each treatment arm with X% increments (increase or decrease) from baseline. The following categories for summary tables are defined:

• $\leq -3*X\%$: Values with more than 3*X% decrease from baseline

• > -3*X% - -2*X%: Values with 2-3*X% decrease from baseline

• > -2*X% - -1*X%: Values with 1-2*X% decrease from baseline

• >-1*X% - 0*X%: Values with 0-1*X% decrease from baseline

• <0*X%- <1*X%: Values with 0-1*X% increase from baseline

Date: 20 Nov 2017 E-Statistical Analysis Plan-17877; Ver.9.0 Supersedes: Ver. 8.0

Page 46 of 80

• 1*X%- < 2*X%: Values with 1-2*X% increase from baseline

• 2*X%- < 3*X%: Values with 2-3*X% increase from baseline

• $\geq 3*X\%$: Values with more than 3*X% increase from baseline

The following % changes will be summarised:

• Heart rate: 50% change

• Blood pressure: 25% change

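### With X = 50%, two of the four decrease bands for WBC, platelets, lactate and heart rate are out of reach, so the banded tables split falls only at 50%

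*SAP*

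**What the plan says.** SAP section 10.3.1 plans a table, for selected laboratory variables, of the number and percentage of patients in each arm by size of percent change from baseline. There are eight bands, four for decreases and four for increases, all in multiples of a variable-specific X. From the deepest upwards, the decrease bands are labelled "Values with more than 3*X% decrease from baseline", "Values with 2-3*X% decrease from baseline", "Values with 1-2*X% decrease from baseline" and "Values with 0-1*X% decrease from baseline". Section 10.4.1 repeats the same bands for vital signs.

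X is then set variable by variable. Section 10.3.1 gives "Platelets: 50% change" and "Lactate: 50% change", with 50% for WBC as well. Section 10.4.1 gives "Heart rate: 50% change". The remaining variables have smaller values: "Hemoglobin: 20% change", 20% for creatinine, 5% for sodium and 25% for blood pressure.

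**The concern.** Rises have no upper limit, whereas falls in a non-negative quantity stop at 100%. A scheme mirrored about zero therefore works for falls only if its deepest cut lies inside 100%. At X = 50% it does not.

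For platelets, white cells and heart rate a fall is a safety-relevant direction. Changes in vital signs and laboratory variables are a safety endpoint in section 2.2.4, and cardiac arrhythmias are a critical adverse event category in Appendix 2. If two arms differ in how deep the falls go, but not in the share of patients crossing 50%, this table shows no difference. For lactate no safety concern about falls is argued; there the point is only that two printed rows cannot be filled.

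**Working it through.** The SAP states no figure to reproduce here. The check puts each X into the stated bands and compares them with the floor for a non-negative measurement.

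**Inputs.** X from sections 10.3.1 and 10.4.1, as listed above. Percent change = 100 × (new − baseline) / baseline. Its minimum is -100%, reached when the new value is zero.

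**Decrease bands.** ≤ -3X; > -3X to -2X; > -2X to -X; > -X to 0.

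| Variable | X | Cut points -X / -2X / -3X | Reachable decrease bands |
|---|---|---|---|
| Sodium | 5% | -5 / -10 / -15% | 4 of 4 |
| Hemoglobin, creatinine | 20% | -20 / -40 / -60% | 4 of 4 |
| Blood pressure | 25% | -25 / -50 / -75% | 4 of 4 |
| WBC, platelets, lactate, heart rate | 50% | -50 / -100 / -150% | 2 of 4, plus exactly -100% |

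At X = 50%:

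- ≤ -150% is impossible.
- > -150% to -100% holds only a change of exactly -100%, that is, a value of zero.
- > -100% to -50% holds every fall of 50% or more short of zero.
- > -50% to 0 holds every smaller fall.

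Falls of 10%, 30% and 49% therefore share one band, and falls of 50%, 60%, 80%, 95% and 99% share the other. The increase side has no such problem: 0 to 50%, 50 to 100%, 100 to 150% and 150% or more can all occur.

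**Condition for the scheme to work.** The deepest cut lies inside the floor when 3X < 100%, so X < 33.3%. Of the values used in the SAP, only 50% fails.

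**Illustration** (baselines chosen here, not taken from the SAP):

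- Platelets 200 to 199: 100 × (-1)/200 = -0.5%. Platelets 200 to 101: 100 × (-99)/200 = -49.5%. Same band.
- Platelets 200 to 99: 100 × (-101)/200 = -50.5%. Platelets 200 to 5: 100 × (-195)/200 = -97.5%. Same band.
- Heart rate 120 to 119: 100 × (-1)/120 = -0.8%. Heart rate 120 to 65: 100 × (-55)/120 = -45.8%. Same band.

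**The case against.** A reader might infer that the tables cannot grade a fall at all, or that a difference between arms in the depth of falls would go unseen in the trial report. The SAP supports neither reading. A working split at -50% remains, and it separates patients who lost half or more of their baseline value from those who did not. Other planned output also shows falls:

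- Sections 10.3.1 and 10.4.1 plan mean, median, interquartile range, minimum and maximum of observed values and of change from baseline at each time point, and counts of clinically significant unanticipated results. Section 10.3.1 adds mean percent change for laboratory variables. Under section 10.1 safety summaries are by arm.
- Sections 10.3.2 and 10.4.2 list every value.
- Section 9.3.1.5 compares individual SOFA scores, coagulation included, and section 9.3.1.6 analyses new dysfunction and failure by organ system.
- Arrhythmias, as critical adverse events, have their own tables and graphs under section 10.2.2.
- Lactate is described in section 9.4.7 and compared as an area under the curve in addendum section 2.6.

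A reader might also infer that the empty rows will be taken as evidence that no large decreases occurred. That is conjecture: rows at -100% and -150% may be recognised as unattainable, and the table shells are in a separate document (section 14), so the final labelling is unknown.

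These objections limit the consequence, and that much stands. They do not repair the table. Minima, quartiles and means do not give the number of patients per arm at successive depths of fall; listings hold the values but do not summarise them. The count of unanticipated results rests on a clinical judgement rather than on depth.

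**Conclusion.** The point holds as a minor error in a descriptive safety format. For 4 of the 8 banded variables, one of the four decrease bands is impossible and another is reachable only at a value of zero. The safety-relevant falls concern three of them: platelets, WBC and heart rate. The table grades their falls only as under 50% or as 50% and over. No hypothesis test, stopping rule, or primary or key secondary result depends on it. The conclusion rests only on the four measurements being non-negative and on percent change being taken relative to baseline, as the band labels state.

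**What to change.** In sections 10.3.1 and 10.4.1, keep the increase bands as they are. For WBC, platelets, lactate and heart rate, replace the decrease cut points with attainable values inside 0 to 100% that retain the -50% cut. One option is -25%, -50% and -75%, which are the cuts the SAP already generates for blood pressure. Leave the variables with X of 5%, 20% or 25% unchanged.

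That example is weaker for heart rate. From a baseline of 120 the three cuts correspond to 90, 60 and 30, so the lowest bands may stay nearly empty, and finer cuts could be used there. The exact values are a matter of choice; the requirement is that they be attainable and fixed before unblinding.

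The cost is a change of SAP wording and one format definition in the table program. No new data are needed. The downside is that the bands are no longer symmetric about zero, so decrease and increase cut points must be labelled separately for these four variables.

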10.3.2 Data Listings

Data listings will be prepared by centre, treatment arm, patient and time-point (including baseline) displaying all laboratory values for all patients.

10.4 Vital Signs (including CVP)

Baseline for all vital signs analyses will be the values obtained at the last assessment prior to the first dose of IMP.

10.4.1 Summary Statistics

Descriptive statistics, i.e., the number of patients with data, mean (standard deviation), median, interquartile range, minimum, and maximum values, will be presented for observed values and change from baseline at each time-point for each vital signs variable.

Furthermore, summary tables will be presented, displaying by time and vital signs parameter, the number of patients with a clinically significant result assessed as unanticipated.

Also, a summary table will be prepared for each vital signs variable that display the number and percentage of patients in each treatment arm with X% increments (increase or decrease) from baseline. The following categories for summary tables are defined:

• $\leq -3*X\%$: Values with more than 3*X% decrease from baseline

• > -3*X% - -2*X%: Values with 2-3*X% decrease from baseline

• > -2*X% - -1*X%: Values with 1-2*X% decrease from baseline

• >-1*X% - 0*X%: Values with 0-1*X% decrease from baseline

• <0*X%- <1*X%: Values with 0-1*X% increase from baseline

Date: 20 Nov 2017 E-Statistical Analysis Plan-17877; Ver.9.0 Supersedes: Ver. 8.0

Page 46 of 80

• 1*X%- < 2*X%: Values with 1-2*X% increase from baseline

• 2*X%- < 3*X%: Values with 2-3*X% increase from baseline

• $\geq 3*X\%$: Values with more than 3*X% increase from baseline

The following % changes will be summarised:

• Heart rate: 50% change

• Blood pressure: 25% change

10.4.2 Data Listings

Data listings will be prepared by centre, treatment arm, patients and time-point (including baseline) displaying all vital signs values for all patients with an indication of abnormal values.

10.5 Episodes of Hypotension

Descriptive statistics of number of patients with episodes of hypotension and the total length of periods with hypotension will be summarized by treatment arm.

The total length of periods with hypotension will be summarized for both all patients, and patients having one or more episodes of hypotension.

Date: 20 Nov 2017 E-Statistical Analysis Plan-17877; Ver.9.0 Supersedes: Ver. 8.0

Page 47 of 80

11 Interim analyses

There will be no interim analyses with the potential to stop the trial early for treatment efficacy. However, once the "burn-in" period in Part 1 (first 200 treated patients) is completed, regular interim analyses will be conducted to improve the efficiency of dose selection and to allow early termination of the part or the trial for futility or for successful dose selection. The following steps will be considered at each interim analysis:

- When 200 patients are treated, the allocation probabilities for the active treatment arms are changed using response-adaptive randomisation (with placebo still 1/3). For the two-thirds of patients assigned to the active arms, the probability that a given active arm is assigned to a patient is proportional to the probability that that arm is the arm with the largest expected number of P&VFD
- Potentially stopping the trial for futility during Part 1. This occurs if no active arm has better than a 5% predictive probability of a significant result in Part 2 if it were to start immediately. This decision can occur at any interim during Part 1 after 200 evaluable patients.
- Potentially ending Part 1 and selecting an active treatment arm to continue to Part 2. This decision can occur at any interim analysis between 300 evaluable and 800 treated patients, and it occurs if some arm has a predictive probability of a successful trial of at least 90% before 800 treated patients, and the threshold drops to 25% for the final Part 1 interim analysis at 800 treated patients. The selected arm is the arm with the largest posterior predictive probability of trial success. This will generally be the best-performing active arm, but if multiple arms are performing equally well, it will be the arm with the lowest dosing level. If Part 1 ends after *N* patients, then Part 2 will consist of up to 1800 *N* evaluable patients.
- If the trial is not stopped for futility or proceeding to Part 2 and active treatment Arm 4 has not yet been approved for assignment of patients, the decision can be made to open up Arm 4. Arm 4 is only opened between 200 evaluable and 600 treated patients and if there is at least a 50% probability that Arm 3 has a higher expected P&VFD than Arm 2 and if data from the lower dosing levels do not suggest any significant safety signals.
- If Part 1 reaches its maximum of 800 treated patients and no arm has a predictive probability of Part 2 success of more than 25%, the trial stops with an inconclusive result and will be interpreted as a standalone Phase 2b trial.

During Part 2, interim analyses will be conducted regularly (until 1600 patients have been treated) to allow early termination of the trial for futility. This occurs if the predictive probability of an overall significant result is less than 5%. In addition, if the predictive probability of observing a more than 2% higher mortality in the active arms compared to placebo is greater than 90% then the trial will stop for futility.

Date: 20 Nov 2017 E-Statistical Analysis Plan-17877; Ver.9.0 Supersedes: Ver. 8.0

Page 48 of 80

12 Deviations from protocol analysis

See change log.

Date: 20 Nov 2017 E-Statistical Analysis Plan-17877; Ver.9.0 Supersedes: Ver. 8.0

Page 49 of 80

13 References

- The EuroQol Group (1990). EuroQol-a new facility for the measurement of health-related quality of life. *Health Policy* 16(3): 199-208
- 2 EuroQoL Home page: http://www.euroqol.org/home.html
- Mehta, C.R. and Pocock, S.J. (2011) Adaptive increase in sample size when interim results are promising: A practical guide with examples. *Statistics in Medicine*, 30, 3267-3284.
- 4 Hochberg (1988). A sharper Bonferroni procedure for multiple tests of significance. *Biometrika* 75(4):800-802
- 5 EMEA. (2000). Points to consider on switching between superiority and non-inferiority. CPMP/EWP/482/99.

Date: 20 Nov 2017 E-Statistical Analysis Plan-17877; Ver.9.0 Supersedes: Ver. 8.0

Page 50 of 80

14 Tables, Listings and Figures

The document with tables, figures and listings (TLF) shells will be presented in a separate document.

Page 51 of 80

Appendix 1 EQ-5D-5L Quality Adjusted Life Year (QALY)

We calculate Quality Adjusted Life Year (QALY) (1), (2) at Day 30 and 180 in three steps:

- (1) A unique EQ-5D-5L health state is defined by combining 1 level from each of the 5 dimensions of EQ-5D-5L. Each health state is referred to in terms of a 5 digit code. For example, state 12345 indicates no problems with mobility, slight problems with washing or dressing, moderate problems with doing usual activities, severe pain or discomfort and extreme anxiety or depression.
- (2) Convert each EQ-5D-5L health state into a single EQ-5D-5L index value. The index values are country specific and we will use the value sets for US and apply these values to all patients in this trial.
- (3) QALY for a patient is then defined to be the area under the curve (AUC) for a Time (with unit of Year) versus index values. AUC will be calculated by the linear trapezoidal method. See below for a schematic presentation where the y-axis is the index value with y_0 , y_1 and y_2 , etc. represent the index values at baseline, Day 30, 60, 90 and 180. The x-axis is Time (in Years) and the t_0 is the start of treatment period, i.e. baseline, and t_1 and t_2 are time of the actual Day 30 and 60, respectively, and so on.

If the index value at baseline is missing then we set QALYs at Day 30 and 180 to missing. No LOCF imputation will be used. However, linear interpolation will be used between data points with missing data in between (e.g. t₀ to t₂, if t₁ is missing).

[figure not shown]

Figure 5: EQ-5D-5L QALY Calculation

Page 52 of 80

Appendix 2 Critical Adverse Events and Classification of Adverse Events Based on Changes in Safety Laboratory Variables

Table 1: Critical Adverse Events

Critical adverse event	MedDRA terms or SMQ used for search				
Potential hypersensitivity reactions	Anaphylactic reaction (SMQ) (Narrow Scope) Angioedema (SMQ) (Narrow Scope)				
Myocardial infarction / ischemia	Ischaemic heart disease (SMQ) (Broad scope)				
Episodes of atrial fibrilation and other cardiac arrythmias	Cardiac Arrhythmias (SMQ) (Broad scope)				
Cerebrovascular accident	Haemorrhagic central nervous system vascular conditions (SMQ) (Broad Scope) Ischaemic central nervous system vascular conditions (SMQ) (Broad Scope) Conditions associated with central nervous system haemorrhages and cerebrovascular accidents (SMQ) (Broad scope)				
Digital ischemia	Peripheral ischaemia Pallor Peripheral coldness				
Renal failure	Acute Renal failure (SMQ)				
Mesenteric ischemia	Ischaemic colitis (SMQ) (Narrow scope)				
Hepato-biliary adverse events	Drug related hepatic disorders - severe events only (SMQ) (Broad Scope)				

Date: 20 Nov 2017 E-Statistical Analysis Plan-17877; Ver.9.0

Supersedes: Ver. 8.0 Page 53 of 80

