9.3.3 Health-Related Quality of Life

9.3.3.1 Change in utility, based on EQ-5D-5L, up to Day 180

EQ-5D-5L will be analyzed by the index value, the overall QALY (Quality-Adjusted Life Years) at Day 30 and 180 (see Appendix 1 for details), and the VAS score.

The QALY scores will NOT be adjusted to e.g. a half yearly time scale at Day 180.

As the QALY is not defined for patients with all remaining values missing, and hence also not defined for those dead, the analyses will automatically only be analyzed for those surviving up until Day 30 and 180 respectively.

For patients with missing baseline index value, the QALY score will also be set to missing. For robustness, a sensitivity analyses will be performed, imputing the missing baseline scores with the overall mean of the baseline health index. Baseline is the timing prior to acute admission.

The QALY at Day 30 and 180 will be compared between treatment arms using an ANCOVA model with baseline health index as covariate, and treatment as factor. Estimated treatment differences (to placebo) along with a 95% confidence interval will be presented.

The index value and VAS scores will be analysed separately for survivors and non-survivors at Day 180 (since all non-survivors will have non-random missing values, and hence would artificially inflate the mean estimates if survivors and non-survivors were analysed together) and will be compared between treatment arms using a repeated measures ANCOVA model with baseline health index/VAS score as covariate, treatment, time and treatment by time interaction as factors, baseline index/VAS score by time interaction, and patient as the experimental unit. Estimated treatment differences (to placebo) along with a 95% confidence interval will be presented for Day 30, 60, 90 and 180. There will be no imputations for missing values.

Page 37 of 80

Furthermore, the QALY, index value and VAS scores will be tabulated treatment arm (including pooled active treatment arms), and the index value and VAS scores will be presented graphically.

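### The Day-30 and Day-180 QALY is an area up to the actual assessment date with no fixed end point, so visit timing enters the score; this is mainly avoidable noise at Day 30

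*SAP*

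**What the plan says.** Appendix 1 gives the definition: "QALY for a patient is then defined to be the area under the curve (AUC) for a Time (with unit of Year) versus index values". The integration rule is "AUC will be calculated by the linear trapezoidal method". The curve starts at start of treatment, and the later time points "are time of the actual Day 30 and 60, respectively, and so on". If an intermediate index is missing, "linear interpolation will be used between data points with missing data in between"; the example given is a line from baseline to Day 60 when Day 30 is absent. The appendix rules out carrying the last observation forward.

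Section 9.3.3.1 states the analysis: "The QALY at Day 30 and 180 will be compared between treatment arms using an ANCOVA model with baseline health index as covariate, and treatment". The model has no other term. The section adds: "The QALY scores will NOT be adjusted to e.g. a half yearly time scale at Day 180". On the population, it says that "the analyses will automatically only be analyzed for those surviving up until Day 30 and 180 respectively".

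Neither place says that the curve is cut at the nominal day, that the area is divided by observed time, or that visit time enters the model.

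**The concern.** A QALY is an index multiplied by a length of time. If the length is each patient's own time to the assessment, two patients with the same health get different scores because they were seen on different days. The analysis then compares these scores as if they covered a common 30 or 180 days. The interval is short at Day 30, so a few days matter proportionally more there.

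The likely cost is lost precision. If one arm's survivors were systematically reached later, that arm would also gain QALYs without better health. Separately, when the Day-30 index is missing, the SAP says how to draw the line but not where the Day-30 area stops.

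**Working it through.** The SAP states no QALY figure, so there is none to reproduce. It gives no index values or visit spread either, so all of those below are assumptions. Time in years is days/365.25.

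**1. Dependence on the visit day.** With constant index u and assessment on day T, QALY = u × T/365.25, which is proportional to T.

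- One day at Day 30: 1/30 = 3.3%.
- One day at Day 180: 1/180 = 0.6%.
- u = 0.7, Day 30: 0.0575 on time, 0.0709 if 7 days late (7/30 = +23.3%).
- u = 0.7, Day 180: 0.3450 on time, 0.3584 if 7 days late (7/180 = +3.9%).
- Index 0.8 at baseline and 0.6 at follow-up: 0.7 × 28/365.25 = 0.0537 if seen on Day 28, and 0.7 × 35/365.25 = 0.0671 if seen on Day 35. The ratio is 35/28 = 1.25.
- With a negative index the direction reverses: u = −0.1 gives −0.0082 on time and −0.0101 if 7 days late.

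**2. Noise at Day 30.** Let m be the mean of the baseline and Day-30 index, and let the visit day be 30 + e, with e independent of health and of SD s. The QALY is m(30 + e)/365.25. The relative increase in ANCOVA residual variance is E[m²]·s² / (30² × residual variance of m).

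Assumptions: baseline mean 0.8 and SD 0.2; Day-30 mean 0.575 (midpoint of 0.55–0.60); residual SD of the Day-30 index 0.25.

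- Residual variance of m = (0.25/2)² = 0.015625; times 900 = 14.06.
- Mean of m = (0.8 + 0.575)/2 = 0.6875; squared = 0.4727.
- If follow-up does not depend on baseline: E[m²] = 0.4727 + 0.01 + 0.0156 = 0.498, so the increase is 0.498/14.06 = 3.5% × s².
- If follow-up moves one for one with baseline: E[m²] = 0.4727 + 0.04 + 0.0156 = 0.528, so the increase is 3.8% × s².

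This gives about 4% for s = 1 day and 14–15% for s = 2 days. Simulating 400,000 survivors under these means and SDs gives 4% and about 15%. In standard-error terms, √1.04 = 1.02 and √1.15 = 1.07.

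**3. Noise at Day 180.** The same kind of simulation gives a 1–8% rise in variance for a visit-date SD of 5–14 days. That is √1.01 to √1.08, or about 0.5–4% in standard error.

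**4. What bias would require.** With mean index 0.7, a one-day difference between arms in mean visit date shifts the Day-30 QALY by 0.7/365.25 = 0.0019. A difference of δ in the Day-30 index shifts it by 15δ/365.25, so one day is equivalent to δ = 0.7/15 = 0.047.

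**5. Missing Day-30 index.** Take 0.8 at baseline and 0.6 on Day 60. The interpolated index at Day 30 is 0.7. Stopping at Day 30 gives 0.75 × 30/365.25 = 0.0616. Running to the next actual point gives 0.7 × 60/365.25 = 0.1150. The SAP does not say which applies.

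**6. Effect of a fixed limit.** Assumed index 0.80, 0.50, 0.60, 0.65, 0.70 at baseline and Days 30, 60, 90, 180:

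| Final visit | As written | Cut at nominal day | Area × nominal/actual |
|---|---|---|---|
| Day 30, on time | 0.0534 | 0.0534 | 0.0534 |
| Day 30, 7 days late | 0.0658 | 0.0557 | 0.0534 |
| Day 30, 14 days late | 0.0783 | 0.0573 | 0.0534 |
| Day 180, on time | 0.3162 | 0.3162 | 0.3162 |
| Day 180, 14 days late | 0.3421 | 0.3154 | 0.3174 |

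Either method removes most or all of the dependence on the visit day. The change left after cutting at Day 30 comes from the interpolated line being less steep when the same index is recorded later.

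**The case against.** Several points on the other side have force.

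- **The no-adjustment sentence.** A reader might infer that the SAP expressly refuses to correct for visit timing. It does not. The sentence names a half-yearly scale at Day 180, mentions neither visit dates nor Day 30, and most naturally means that scores are not converted to a standard time unit. What stands is that no other text standardises the interval.
- **The wording of the time points.** It could mean calendar Day 30 rather than the visit date, and Figure 5, which illustrates the calculation, was not available for this check. The visit-date reading is the more natural one. On the calendar reading, the SAP would still need a rule for the index on that day when the assessment falls on another.
- **Size.** Visit windows normally stand in the protocol, which is not at hand. A reader could extend the calculation to a visit-date SD of 5 days and report a 94% rise in variance, but nothing in the SAP supports that spread.
- **Bias.** A reader might infer a biased treatment comparison. The trial is double-blind, and the SAP gives no reason to expect visit timing to differ by arm.
- **Stakes.** The endpoint is not a key secondary one (Section 2.2.3) and lies outside the Hochberg procedure in Section 9.3. The index and VAS are also analysed by repeated measures and do not accumulate with time. The health-economic evaluation is reported separately (Section 2.2.5).
- **The remedy.** Holding the last index up to the cut would conflict with the appendix's bar on carrying observations forward, and requiring a later assessment would cost some patients their value. A workable fix has to avoid both.

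**Conclusion.** The point holds as a minor one. Followed as written, on its natural reading, the rule makes the QALY proportional to the time to the assessment for a given mean index, and nothing in the SAP offsets this. The per-day figures of 3.3% and 0.6% are arithmetic and hold for any constant positive index. The loss of precision at Day 30, about 4% in residual variance for a visit-date SD of 1 day and about 15% for 2 days, rests on assumed index means, SDs and visit spreads. At Day 180 the effect is small. The documents do not support a claim of bias, which would need timing to differ between arms. The undefined end of the Day-30 area when that index is missing is a separate gap in the same rule.

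**What to change.** Amend Appendix 1 to keep the actual assessment dates as the positions of the points, but integrate from Day 0 to exactly Day 30 (30/365.25 years) and exactly Day 180 (180/365.25 years). Obtain the index at the cut by linear interpolation between the assessments on either side. This also settles the missing Day-30 case, because the line from baseline to Day 60 is simply cut at Day 30.

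Where the scheduled assessment took place before the cut and no later one exists, multiply the area by nominal over actual days (for example 30/actual day). An early Day-180 visit will always fall here, since Day 180 is the last time point listed. No such patient loses a value, and the bar on carrying observations forward stands. Patients whose QALY the SAP already treats as undefined or missing stay so.

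The cost is a short addition to Appendix 1, a little extra programming, and a mild assumption for patients last assessed just before the cut: that their average index to that visit also applies to the remaining days.
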